### **Survey administration**

The electronic survey was created using Qualtrics survey software and responses were automatically captured on the Qualtrics platform. Completed survey responses were exported from Qualtrics to SPSS software for statistical analysis.

The survey was distributed on 2/9/2020. The closing date for the survey was 2/10/2020. The hyperlink remained active for a few days after the closing date to allow for any late responders due to the COVID pandemic.

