## **Statistical analyses**

Only completed surveys will be analysed. The survey data will be analysed using descriptive and inferential statistics. Descriptive statistics will include analysis of categorical and continuous data. Descriptive statistics of categorical variables will be frequency analysis i.e., percentage of the different categories within each variable. For example, proportion of Hospital Teams that are Routinely Admitting Teams and Non-Routinely Admitting Acute Teams. Categorical data will be visualised with bar and pie charts. The evaluation method for continuous data (incidence of pneumonia) will be mean and standard deviation to evaluate the dispersion of pneumonia incidence across the hospital teams and visualised using histograms.

Inferential statistics (linear regression analysis) will be used to test the hypotheses and explore if there is an association between the dependent variable (incidence of stroke-associated pneumonia) and independent binary variables: 1. Hospital Teams that use Water only dysphagia screening protocols (DSP) versus Hospital Teams that use water and other consistencies DSPs, 2. Hospital teams that use written guidelines for the first specialist clinical bedside swallow assessment versus Hospital teams that do not use written guidelines for the first specialist swallow assessment, 3. Hospital Teams that insert Nasogastric Tubes (NGTs) overnight have increased risk of SAP compared to Hospital Teams that do not insert NGTs overnight and 4. Hospital Teams with a written oral care protocol versus those do not have a written oral care protocol. Linear regression analysis will be visualised using Model Summary tables with Coefficients and 95% Confidence Intervals.

The proposed analysis for each variable is given in Table 1.

Table 1 – Proposed analysis for each variable

Variable	Data Source (s)	Values	Type of variable	Analysis approach	Methods for summarising data
Hospital Team	Survey Question #3 Please type the name of your hospital and select from the drop-down menu. SSNAP 2019 Team Centred 72-hour cohort data	1 = Routinely Admitting Team 2 = Non-Routinely Admitting Team	Categorical – Nominal - dichotomous	Descriptive statistics (frequencies) - Proportion of completed surveys for Routinely Admitting Team and Non-Routinely Admitting Acute Teams by SCN Region	Table

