Time from decision to non-orally feed and feeding by NGT	Survey Question #32 In patients who are unable to maintain adequate nutrition and fluids orally, please indicate typically the number of hours from when the decision is taken to non-orally feed and the beginning of feeding by an NGT?	1=< 6 hours 2>= 6 - < 12 hours 3>= 12 - < 24 hours 4>= 24 - < 48 hours	Categorical - Nominal	Descriptive statistics (frequencies) - Proportion by selected choice	Bar chart
Confirmation of position of NGT	Survey Question #33 How does your stroke unit check the position of the NGT before starting feeding?	1= pH testing of NGT aspirate, 2= Chest radiography if no aspirate obtained or pH above recommended level, 3= Routinely perform chest radiography, 4= Other	Categorical - Nominal	Descriptive statistics (frequencies) - Proportion by selected choice	Pie Chart/Free text
Management strategies	Survey Question #34 In cases of inadvertent NGT removal, does your stroke unit typically use any of the following management strategies?	1= Mittens, 2= Nasal retention device, 3= 1:1 staff: patient supervision, 4=Other	Categorical - Nominal	Descriptive statistics (frequencies) - Proportion by selected choice	Pie Chart/Free text

Maximum number of NGTs	Survey Question #36 In case of inadvertent NGT removal, what is the maximum number of times reinsertion of the NGT is attempted in any patient?	1=Once, 2= Twice, 3= Three times, 4= If more than three, please state how many	Categorical – Ordinal	Descriptive statistics (frequencies) - Proportion by selected choice	Pie Chart/Free text
Overnight NGT insertion	Survey Question #37 Are NGTs inserted overnight? SSNAP 2019 Patient Centred Post 72hr cohort data prescription of antibiotics for a newly diagnosed pneumonia	1=Yes 2=No  SPSS Recoded (dummy) variables  0=Yes 1=No	Categorical – Nominal – dichotomous  Dependent variable – outcome - incidence of SAP Independent variable – predictor – Insertion of NGT overnight	Descriptive statistics (frequencies) - Proportion answering yes or no AND Inferential statistics (Linear Regression) Hypothesis – Hospital Teams that insert NGTs overnight have increased risk of SAP compared to Hospital Teams that do not insert NGTs overnight.	Bar chart  Model Summary Table with coefficients and 95% Confidence Intervals

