## Data sets

Data from the Sentinel Stroke National Audit Programme registry will be used ([www.strokeaudit.org](http://www.strokeaudit.org)). Data will include administration of antibiotics for a new clinical diagnosis of pneumonia in the first 7 days after admission (Patient Centred Post 72-hour data) and Key indicators 4.5 Percentage of applicable patients who were given a swallow screen within 4h of clock start and 4.6 Percentage of applicable patients who were given a formal swallow assessment within 72h of clock start (Team Centred results). 2019 quarterly data will be used to create an annual 2019 data set.

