## Method for analysing the data for incidence of stroke-associated pneumonia

Stroke-associated pneumonia (SAP) will be defined as the administration of antibiotics for a new clinical diagnosis of pneumonia in the first 7 days after admission as determined by the treating physician. SSNAP Patient Centred Post 72-hour quarterly data for Antibiotics for newly acquired pneumonia in the first 7 days from clock start will be used to calculate an annual 2019 pneumonia percentage for each team to measure the dispersion of the of pneumonia incidence across the teams.

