## **Sensitivity analysis**

Sensitivity analysis will be undertaken to understand how certain values contribute to the overall uncertainty of the model. For example, the impact of a lower-than-average response rate from a particular SCN region or the latest SSNAP annual data which includes data for the Covid-19 period compared to 2019 data (pre Covid-19).

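### The default 95% CI for team pneumonia percentages assumes equal variance and can be slightly off if a minority practice tracks team size; naming the Welch interval is a cheap fix (minor)

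*SAP*

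**What the plan says.** The SAP's section on the method for analysing incidence reduces each team to a single number, "an annual 2019 pneumonia percentage for each team to measure the dispersion of the of pneumonia incidence across the teams". Under Statistical analyses that number is treated as continuous ("The evaluation method for continuous data (incidence of pneumonia) will be mean and standard deviation"). It then becomes the outcome of a linear regression meant to test the hypotheses and "explore if there is an association between the dependent variable (incidence of stroke-associated pneumonia) and independent binary variables". The reporting rule is: "Linear regression analysis will be visualised using Model Summary tables with Coefficients and 95% Confidence Intervals".

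Table 1 repeats the regression in a separate row for each of the four practices (the oral care row says only regression). The hypotheses compare teams, for example "Hospital Teams that insert NGTs overnight have increased risk of SAP compared to Hospital Teams that do not insert NGTs overnight".

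No section names robust standard errors, an unequal-variance interval, weights or a check of equal variance. The Sensitivity analysis section is general ("Sensitivity analysis will be undertaken to understand how certain values contribute to the overall uncertainty of the model"), and its two examples concern regional response and Covid-period data.

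**The concern.** Ordinary linear regression assumes that every observation has the same residual variance. Percentages from teams of different size do not meet that assumption, because a small team's percentage carries more sampling noise. With one binary predictor, the regression is the pooled-variance comparison of two groups of teams. If one practice group contains relatively more small teams, its variance is larger, and pooling gives the wrong standard error unless the groups are about equal in number.

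The 95% CI is the only inferential output that the SAP specifies for the four hypotheses. The error could go either way: too narrow if a minority practice sits mainly in small teams, too wide if it sits mainly in large ones. A method that holds in both cases is best named beforehand.

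**Working it through.** **No figure to reproduce.** The SAP gives no sample size calculation, SD, team size or practice share, so the check is of how the specified interval behaves.

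**Inputs from the SAP.** At most 166 teams (Response rate); 14% incidence (Research background, a literature figure and not a team rate).

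**Assumed inputs.** Patients per team, between-team SD and practice shares.

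**Variance of one team's percentage.** In squared percentage points it is (between-team SD)² + 100² × p(1-p)/n. With p = 0.14, the second term is 1204/n. For an assumed between-team SD of 3 points:
- n = 100: 9 + 12.04 = 21.04
- n = 500: 9 + 2.41 = 11.41
- ratio: 21.04/11.41 = 1.84

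**Effect on the interval.** The true variance of the difference is v1/n1 + v0/n0. The pooled version is s² × (1/n1 + 1/n0), with s² = [(n1-1)v1 + (n0-1)v0]/(n1+n0-2). Here n1 and n0 are numbers of teams. Approximate coverage is 2Φ(1.96 × pooled SE/true SE) - 1. With 166 teams:

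| Case | v1, n1 | v0, n0 | True SE | Pooled SE | Ratio | Coverage |
|---|---|---|---|---|---|---|
| Even split, fully sorted by size | 21.04, 83 | 11.41, 83 | 0.625 | 0.625 | 1.00 | 95% |
| Practice in 20% of small and 10% of other teams | 15.85, 22 | 14.07, 144 | 0.905 | 0.865 | 0.96 | 93.9% |
| 20% minority, all small teams | 21.04, 33 | 11.41, 133 | 0.850 | 0.709 | 0.83 | 89.8% |
| 20% minority, all large teams | 11.41, 33 | 21.04, 133 | 0.710 | 0.851 | 1.20 | 98.1% |

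In the second row 30% of teams are small, so the practice share is 0.3 × 0.2 + 0.7 × 0.1 = 13%, or 22 teams. Small teams make up 6/13 = 46% of the practice group and 24/87 = 28% of the rest. Hence v1 = 0.46 × 21.04 + 0.54 × 11.41 and v0 = 0.28 × 21.04 + 0.72 × 11.41, using unrounded shares. The last two rows sort teams completely by size and are deliberate extremes.

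**Simulation.** Data were generated with no true effect, 14% mean incidence, and beta-distributed team risks with SD 2, 3 or 4 points. There were 166 or 113 teams, four assumed size distributions, and 2,000 data sets in each of 216 scenarios, run twice. Coverage of the ordinary 95% CI was:
- practice unrelated to size: 93.9-96.2%
- common practice (50% of small v 30% of other teams, or 60% v 40%): 93.5-96.3%
- minority practice mildly commoner in small teams (20% or 25% v 10%): 92.6-95.0% with log-normal sizes (median 400), 91.7-95.1% if 30% of teams have median 100, and 91.0-94.2% if 30% have median 50
- extreme small-team minority (40% v 3%): 91.0-93.4%, 88.4-93.2% and 85.3-90.2% for the same three size distributions
- minority practice in large teams: 94.9-97.3% (10% of small v 20% of other teams) or 95.6-99.0% (1% v 20%)

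A further simulation with 113 teams and 4,000 data sets per cell gave the same pattern: about 94-95.5% when practice is unrelated to size or common, 92-95% for a mild small-team minority, 86-94% for an extreme one, and 96-99% for a large-team minority.

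**Alternatives.** The Welch interval covered 94-96% throughout the 113-team simulation and 93.3-96.3% over the wider grid. HC3 covered 93.5-96% and 92.6-96.4% respectively. With all four predictors in one model, ordinary intervals covered 85.4-98.6% and HC3 93.1-96.7%. The mean coefficient error was at most 0.08 points, so the estimate itself is not biased by this.

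**The case against.** The strongest reply is that the SAP states nothing false. The sentence on coefficients and intervals describes output, the standard error is an implementation detail, and the harm needs facts the document does not supply: a minority practice, a link between that practice and team size, and an appreciable share of small teams. The Sampling plan also limits inclusion to active units with enough records to report, which makes a large share of very small teams less likely, although no threshold is given. In the mild scenarios the shortfall is only one to three coverage points. All of this stands, and it is why the point is minor. What remains is that the plain reading of an unqualified linear regression is equal variance, and a better interval is available at almost no cost.

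Three stronger readings are tempting, and the document supports none of them:
- **A reader might infer that coverage could be very poor.** A figure as low as 77.5% does arise, but only with no between-team variation and complete sorting of a 10% minority into the smallest teams. Nothing in the SAP suggests this.
- **A reader might infer that equal weighting is the fault and that teams should be weighted by size.** The hypotheses compare teams, so equal weighting fits the question. Weighting changes the target when effects vary with size. For an assumed effect of 4 points in the smallest 30% of teams and none elsewhere, equal weights estimate 0.3 × 4 = 1.2 points, and patient-count weights 0.4 or less. The SAP also does not say that per-team counts are in hand, and weighting is not needed to correct the interval.
- **A reader might infer that HC3 should be used throughout.** For a practice held by 10% of teams and unrelated to size, HC3 covers 93-95%, against 94-96% for the ordinary and Welch intervals. Welch is the better default for a single predictor.

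**Conclusion.** The point holds in a conditional form and is minor. As written, the SAP's default is a pooled-variance interval on percentages whose variance depends on team size. The size of the error rests on assumed team sizes, practice shares and between-team SD, and cannot be settled from the document. It may be nil for all four practices. The result does not call the planned coefficients or the team-level comparison into question, and it says nothing about confounding by team size or case mix, which neither Welch nor HC3 would address.

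**What to change.** In the SAP, Statistical analyses, add one sentence: the equal-weight team-level comparison is kept; the 95% CI for each single binary predictor is the unequal-variance (Welch) interval; and HC3 standard errors are used if the four predictors are fitted in one model. Apply the same wording to the four regression rows of Table 1.

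The cost is small. The coefficient is unchanged, and no new survey data or patient counts are needed. For a single predictor the interval follows from each practice group's mean, SD and number of teams, so the software is no obstacle ("Completed survey responses were exported from Qualtrics to SPSS software for statistical analysis"). The downside is output slightly less simple than the default SPSS regression table. The Sensitivity analysis section needs no change on this account.

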	Survey Question #9 Does the dysphagia screening protocol only use water (Level 0 Thin Fluids) i.e., 100% water? SSNAP 2019 Patient Centred Post 72hr cohort data prescription of antibiotics for a newly diagnosed pneumonia	1= Yes 2= No  SPSS Recoded (dummy variables) 0=Yes 1=No	Categorical – Nominal - dichotomous  Dependent variable – outcome - incidence of SAP Independent variable – predictor – Water only DSPs versus water and other consistencies DSPs	Descriptive statistics (frequencies) - Proportion answering yes or no AND Inferential statistics (Linear Regression) Null hypothesis – There is no difference in incidence of pneumonia using a dysphagia screen that uses 100% water compared to water and other consistencies	Bar chart  Model Summary Table with coefficients and 95% Confidence Intervals
	Survey Question #10 What is the maximum amount of water given? Please indicate the maximum amount in millilitres (mls).	1=5, 2=10, 3=15, 4=20, 5=25, 6=50, 7=100, 8=150, 9=200	Categorical Ordinal	Descriptive statistics (frequencies)- proportion by selected choice	Bar chart

	Survey Question #11 Which International Dysphagia Diet Standardisation Initiative (IDDSI) levels are included in the dysphagia screening protocol?	1= Level 0 Thin, 2= Level 1 Slightly Thick, 3=Level 2 Mildly Thick, 4=Level 3 Moderately Thick, 5=Level 4 Puree, 6=Level 5 Minced and Moist, 7=Level 6 Soft & Bite Size, 8=Level 7 Regular Easy to Chew, 9=Level 7 Regular	Categorical – Ordinal	Descriptive statistics (frequencies) - Proportion by selected choice	Bar chart
	Survey Question #12 Which IDDSI level consistency do you screen with first?	1= Level 0 Thin, 2= Level 1 Slightly Thick, 3=Level 2 Mildly Thick, 4=Level 3 Moderately Thick, 5=Level 4 Puree, 6=Level 5 Minced and Moist, 7=Level 6 Soft & Bite Size, 8=Level 7 Regular Easy to Chew, 9=Level 7 Regular	Categorical – Ordinal	Descriptive statistics (frequencies) - Proportion by selected choice	Bar chart
Delays in dysphagia screening	Survey Question #14 Below is a list of reasons for delays in stroke patients being screened for dysphagia. How applicable are each of these reasons for delays in stroke patients being screened for dysphagia in your stroke unit?	1=Strongly applicable 2=Somewhat applicable 3=Somewhat less applicable 4=Strongly not applicable	Categorical – Nominal	Descriptive statistics - Likert Scale	Bar chart/Free text

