	SSNAP 2019 Patient Centred Post 72hr cohort data prescription of antibiotics for a newly diagnosed pneumonia	SPSS Recoded (dummy) variables 0=Yes 1=No	outcome - incidence of SAP Independent variable – predictor – Written guidelines (versus clinical reasoning and hypothesis generation)	Null hypothesis – Using written guidelines for the first specialist swallow assessment will not be associated with incidence of pneumonia	coefficients and 95% Confidence Intervals
Components of the specialist swallow assessment	Survey Question #21 In your Stroke Unit, what does the first clinical (bedside) swallow assessment typically involve?	1= PMH, 2= HPC, 3= Assessment of cognitive-communication status, 4= Assessment of respiratory status, 5= Cranial Nerve examination, 6=Cough reflex testing, 7= Assessment with oral intake 8= Assessment with postural strategies, 9= Assessment with swallowing manoeuvres, 10= Other	Categorical – Nominal	Descriptive statistics (frequencies) – Proportion by selected choice	Bar chart/Free text
	Survey Question #22 What International Dysphagia Diet Standardisation Initiative (IDDSI) levels are typically included in the first clinical (bedside) swallow assessment?	1=Level 0 Thin, 2= Level 1 Slightly Thick, 3= Level 2 Mildly Thick, 4=Level 3 Moderately Thick, 5= Level 4 Puree, 6=Level 5 Minced and Moist, 7=Level 6 Soft & Bite Sized, 8= Level 7 Easy to Chew, 9=Level 7 Regular	Categorical – Ordinal	Descriptive statistics (frequencies) - Proportion by selected choice	Bar chart
	Survey Question #23 Please describe what postural techniques are assessed? Examples include chin-down posture, chin-up posture, head	Free text		Free text	

	rotation (turn to side) and head tilt. These examples are not exhaustive.				
	Survey Question #24 Please describe what swallowing manoeuvres are assessed? Examples of include effortful swallow, Mendelsohn manoeuvre, supraglottic swallow and super-supraglottic swallow. These examples are not exhaustive.	Free text		Free text	
Delays in specialist assessment	Survey Question #25 Below is a list of reasons for delays in stroke patients receiving a clinical (bedside) swallowing assessment. How applicable are each of these reasons for delays in stroke patients receiving a clinical swallowing assessment in your stroke unit?	1=Strongly applicable 2=Somewhat applicable 3=Somewhat less applicable 4=Strongly not applicable	Categorical – Nominal	Descriptive statistics - Likert Scale	Bar chart/Free text

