Positioning during NGT feeding	Survey Question #38 Where 0 degrees is lying flat and 45 degrees is sat upright, what is the standard position in which the patient is positioned during NGT feeding?	1=0 degrees 2= > 0 - < 30 degrees 3= ≥ 30 - < 45 degrees 4= 45 degrees 5= Other (please state)	Categorical - Ordinal	Descriptive statistics (frequencies) - Proportion by selected choice	Bar chart/Free text

Oral Care Protocol	Survey Question #39 Does your stroke unit have a written oral care protocol?	1=Yes 2=No  SPSS Recoded (dummy) variables  0=Yes 1=No	Categorical – Nominal – dichotomous  Dependent variable – outcome - incidence of SAP Independent variable – predictor – written oral care protocol	Descriptive statistics (frequencies) - Proportion answering yes or no AND Inferential statistics (Regression) Hypothesis - Hospital Teams with a written oral care protocol will have reduced rates of incidence of SAP compared to those that do not have a written oral care protocol	Bar chart  Model Summary Table with coefficients and 95% Confidence Intervals
	Survey question #40 Is this protocol a hospital oral care protocol or a specific protocol written for the oral care of stroke patients on your unit?	1=Hospital oral care protocol, 2= Stroke oral care protocol	Categorical – Nominal - dichotomous	Descriptive statistics (frequencies) – Proportion by selected choice	Bar chart
Oral care provision in H/ASU	Survey question #41 Are there differences in oral care provision for patients in the hyper/acute stroke unit compared to those patients in other parts of the stroke pathway?	1=Yes 2=No	Categorical – Nominal - dichotomous	Descriptive statistics (frequencies) – Proportion answering yes or no	Bar chart

	Survey question #42 How is oral care provision in the hyper/acute stroke unit different to that provided post-acute phase stroke?	Free text		Free text	
Oral care provision for dysphagic patients	Survey question #43 Are there differences in oral care provision for patients with dysphagia?	1=Yes 2=No	Categorical – Nominal – dichotomous	Descriptive statistics (frequencies) – Proportion answering yes or no	Bar chart
	Survey question #44 If yes, please describe what differences there are in oral care provision for people with dysphagia compared to the provision for those people without dysphagia.	Free text		Free text	

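### Table 1 points to four one-predictor regressions and the SAP never commits to mutual adjustment, so correlated practices would confound each other's coefficients

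*SAP*

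**What the plan says.** The Statistical analyses section sets out the inferential method in one sentence: "Inferential statistics (linear regression analysis) will be used to test the hypotheses and explore if there is an association between the dependent variable" and the four predictors, which follow as a numbered list ("incidence of stroke-associated pneumonia) and independent binary variables: 1. Hospital Teams that use Water only dysphagia screening protocols (DSP", and so on to the fourth). It does not say whether the four enter one model or four.

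The section then refers the detail to Table 1: "The proposed analysis for each variable is given in Table 1". Each hypothesis has a separate row there, with one predictor:

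- Survey Question #9 (Hypothesis 1): "Independent variable – predictor – Water only DSPs versus water and other consistencies DSPs"
- Survey Question #20 (Hypothesis 2): "Written guidelines (versus clinical reasoning and hypothesis generation"
- Survey Question #37 (Hypothesis 3): "Independent variable – predictor – Insertion of NGT overnight"
- Survey Question #39 (Hypothesis 4): "Independent variable – predictor – written oral care protocol"

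Each of these rows carries its own hypothesis and its own model summary table with coefficients and confidence intervals. The text also speaks of such tables in the plural: "Linear regression analysis will be visualised using Model Summary tables with Coefficients and 95% Confidence Intervals". No section names an adjustment variable, an adjusted estimate or a multivariable model.

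**The concern.** One respondent per stroke unit answers all four questions, so the four exposures are features of the same teams. If they are associated across teams, a regression on one of them cannot tell its association with pneumonia from that of the practices left out. One real association could then appear under more than one hypothesis, or one could mask another. Hypotheses 1 to 4 each concern a named practice, so the reader will take each coefficient as belonging to that practice.

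The open wording has a cost of its own. The SAP describes the survey, which closed on 2/10/2020, in the past tense, and it takes the outcome from 2019 audit data. A choice between one model and four that is not written down could be settled with results in view. Nothing in the document suggests that it was.

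**Working it through.** **Inputs from the SAP.** There are four binary team-level predictors and at most 166 teams (Sampling plan). The number of completed surveys is not given. The SAP states no power calculation, effect size, standard deviation, practice prevalence or correlation between practices, so there is no figure of its own to reproduce. All effect, correlation, prevalence and SD values below are assumptions.

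**Step 1: which model is planned.** Text: one outcome, four numbered predictors, and no statement of how they combine. Table 1: one predictor, one hypothesis and one model summary per row. Elsewhere: no covariates. The evidence favours four one-predictor models without stating them.

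**Step 2: bias of an unadjusted coefficient.** For practice 1, the expected unadjusted coefficient is

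β₁ + Σⱼ βⱼ × δⱼ,

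where the sum runs over the omitted practices and δⱼ is the slope of practice j on practice 1. For binary variables of equal prevalence, δⱼ equals their phi correlation. If one omitted practice has a 1.5-point association:

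- phi = 0: 1.5 × 0 = 0 points
- phi = 0.2: 1.5 × 0.2 = 0.3 points
- phi = 0.4: 1.5 × 0.4 = 0.6 points

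A negative phi reverses the sign. Two omitted practices with associations of +1.5 and −1.5 and the same phi cancel: at phi = 0.3, 0.45 − 0.45 = 0.

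**Step 3: scale.** Assume a between-team SD of 4 points, all 166 teams responding and an even split. The 95% half-width is then about 1.96 × 2 × 4/√166 = 1.22 points. A bias of 0.3 to 0.6 is a quarter to a half of that (0.3/1.22 = 0.25; 0.6/1.22 = 0.49).

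**Step 4: cost of adjusting.** With four predictors and a common correlation ρ, the variance inflation factor is 1/(1 − 3ρ²/(1 + 2ρ)).

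| ρ | 3ρ²/(1 + 2ρ) | VIF | SE multiplier |
|---|---|---|---|
| 0.2 | 0.086 | 1.09 | 1.05 |
| 0.3 | 0.169 | 1.20 | 1.10 |
| 0.4 | 0.267 | 1.36 | 1.17 |

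**Step 5: a deliberately unfavourable illustration.** A simulation (3,000 runs per setting) assumed 50% prevalence of each practice, no association for the practice tested, 1-point associations for all three others in the same direction, residual SD 4 and two-sided 5% tests. The bias is then 3 × ρ × 1 point.

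| ρ | Bias (points) | False-positive rate, one predictor, 166 teams | Same, 83 teams |
|---|---|---|---|
| 0 | 0 | 5% | 5% |
| 0.1 | 0.3 | 7% | 6% |
| 0.3 | 0.9 | 29% | 16% |
| 0.5 | 1.5 | 65% | 37% |

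With all four predictors in the model, the bias was about zero and the false-positive rate about 4% to 6% throughout. The same-direction pattern does not match the SAP's own hypotheses: Hypothesis 3 expects more pneumonia, Hypothesis 4 less, and Hypotheses 1 and 2 are stated as nulls. The table shows the mechanism and is not a forecast.

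**The case against.** The strongest reply is that the SAP never says the models are separate. Table 1 works through the survey variable by variable, so one predictor per row is what one would see under either approach. The numbered list fits a joint model, and the Sensitivity analysis section speaks of a single model. This stands as far as it goes: a reader might infer that the SAP fixes four univariable regressions, and it does not. But if a joint model is meant, it is nowhere stated, and the same edit is needed.

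Second, a reader might infer that the four practices are known to occur together, as signs of a formalised, well-staffed unit. The SAP has no such data. Question #9 asks whether the screen uses water only, which is not a measure of formality; whether a written protocol exists is Question #4, which is only described. For overnight tube insertion, the rationale cites safety advice linking placement to senior support. A protocol-driven unit might insert fewer tubes overnight and a better-staffed one more, so the sign is open. This objection stands in full.

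Third, the primary outcome and the analysis text speak of association, and an unadjusted comparison of teams does answer a question of association. That is fair, but the research question asks how variation in practice affects pneumonia, and four unadjusted answers cannot be read practice by practice if the practices cluster.

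Fourth, mutual adjustment does not deal with a common cause outside the four variables, such as staffing or case mix. This is correct and limits what the change achieves.

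**Conclusion.** The point holds in a limited form. Table 1 indicates four one-predictor regressions, and the SAP nowhere commits to mutual adjustment. To the extent that the practices are correlated, each unadjusted coefficient takes up a share of the others' associations.

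A reader might go further and conclude that each coefficient absorbs the full effects of the other three practices. The documents do not support that. The share is proportional to the correlation, is zero if the practices are uncorrelated, can have either sign, and can cancel.

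For one other practice with a 1.5-point association and phi of 0.2 to 0.4 at equal prevalence, the share is 0.3 to 0.6 points. Every value behind that range is assumed. The comparison with a half-width of about 1.2 points further assumes an SD of 4 and a full response. The case for change rests on the low cost of a joint model on data already collected, not on any demonstrated bias.

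**What to change.** State in the Statistical analyses section and in the four hypothesis rows of Table 1 that Hypotheses 1 to 4 are tested in one linear regression containing all four binary predictors. Report the four unadjusted estimates beside it, and tabulate the pairwise associations between practices so that readers can see how much the adjustment could matter.

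Add a rule for teams without a Question #9 value, for example because they have no screening protocol. The SAP describes forced responses and no skip rule, so there may be no such teams. If there are, a three-predictor model for Hypotheses 2 to 4 would allow them to be included.

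The cost is SAP wording and one further model, with confidence intervals about 5% to 17% wider at correlations of 0.2 to 0.4. The SAP should also say that the joint model addresses confounding among the four practices only, and leaves confounding by case mix or unit staffing untouched.
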